#### **6.4.2. Additional considerations**

- The safety analysis will be performed for each vaccination dose separately ie pregnancy dose and post-delivery dose.
- The percentage of infants with unsolicited symptoms occurring from delivery until 2 months with its exact 95% CI will be tabulated by preferred term. Similar tabulation will be done for Grade 3 unsolicited symptoms and for unsolicited symptoms possibly related to vaccination.
- The summary on concomitant medication (i.e. any medication, antipyretic medication, prophylactic antipyretics) will be performed over the 8 day period instead of 4 days.
- All SAEs will be summarized without distinction of SAEs possibly related to GSK concurrent medication.
- The analysis of safety in the household contacts will be performed on the vaccinated household contacts instead of the Total cohort for household contacts in Spain.

## **7. ANALYSIS INTERPRETATION**

For analysis on the primary objective with pre-defined success criteria and an appropriate type I error control, appropriate conclusion can be drawn.

The secondary objectives of the study are descriptive and should be interpreted as such.

## 8. CONDUCT OF ANALYSES

### 8.1. Sequence of analyses

Description	Analysis ID	Disclosure Purpose (IN=internal, CTRS=public posting, SR=study report and public posting)	Dry run review needed (Y/N)	Study Headline Summary (SHS)requiring expedited communication to upper management (Yes/No)	Reference for TFL
Final	E1_01	SR	Yes	Yes	TFL TOC

### 8.2. Statistical considerations for interim analyses

No statistical interim analysis will be performed.

## 9. CHANGES FROM PLANNED ANALYSES

- During the course of the study, the assays used to measure the anti-D, anti-T, anti-PT, anti-FHA and anti-PRN IgG concentrations were re-developed and re-validated and both assay units and assay cut-offs were adapted. The new ELISA’s for PT, FHA and PRN were calibrated against the WHO International Standard (NIBSC 06/140). This allowed the expression of concentrations measured with the new ELISA’s in international units per milliliter (IU/mL) instead of the formerly used ELISA units per milliliter (ELU/mL). The newly validated DTPa ELISA’s used in the study have a lower assay cut-off as compared to the one described in the protocol. The current assay cut-off is 0.057 IU/mL for anti-D, 0.043 IU/mL for anti-T, 2.693 IU/mL for anti-PT, 2.046 IU/mL for anti-FHA and 2.187 IU/mL for anti-PRN. An agreement between the old and new ELISAs was shown with regards to the two thresholds of clinical relevance for the DI/TE response (0.1 IU/mL and 1.0 IU/mL) and therefore the clinical endpoints and anti-D and anti-T are unchanged. In the absence of a correlate of protection for the *B. pertussis* antigens, the pertussis endpoints were redefined based on the assay cut-off.
- Refer to section [6.1.2](#), [6.3.2](#) and [6.4.2](#) for other changes.

## 10. LIST OF FINAL REPORT TABLES, LISTINGS AND FIGURES

The TFL TOC provides the list of tables/listings and figures needed for the study report. It also identifies the tables eligible for each analyses and their role (synopsis, in-text, post-text, SHS, CTRS,...). Note that all TFL aimed to be included as post-text are noted as post-text even if these are tabulation of individual data such as listing of SAE. The post-text material contains all source material for the study report and accordingly a post-text table may be redundant with an in-text table.

Add the text below as applicable

The mock tables referred under column named ‘layout’ can be found in legacy-NV/GSK SDD dedicated folder for standard tables and in section 12 for study specific mock table/figure/listing. The latter table/figure/listing are identified by the prefix SS\_ in the TFL Toc.

The following group names will be used in the TFL TOC:

Group order in tables	Group label in tables	Group definition for footnote	Pooled Groups label in tables	Pooled definition for footnote
1	dTpa Group	Mothers received dTpa during pregnancy	NA	NA
2	Control Group	Mothers received placebo during pregnancy	NA	NA

If sub-groups are defined in the protocol, you can use the following example to describe these.

The following sub-group names will be used in the TFLs

Sub-group order in tables	Sub-group label in tables	Sub-group definition for footnote
1	18-24Y	18-24 years old subjects
2	25-34Y	25-34 years old subjects
3	35-45Y	35-45 years old subjects
4	27-32W	27-32 weeks of gestation of foetus at dose 1
5	33-36W	33-36 weeks of gestation of foetus at dose 1

## **11. ANNEX 1 STANDARD DATA DERIVATION RULE AND STATISTICAL METHODS**

### **11.1. Statistical Method References**

The exact two-sided 95% CIs for a proportion within a group will be the Clopper-Pearson exact CI [Clopper CJ, Pearson ES. The use of confidence or fiducial limits illustrated in the case of binomial. *Biometrika*. 1934;26:404-413].

The 95% CIs of the group GMC ratios will be computed using an ANOVA model on the logarithm10 transformation of the concentrations. The ANOVA model will include the vaccine group as fixed effects. The CI of the group GMC ratios will be computed using a two-sample Welch's t test assuming heterogeneity of variance.

The 95% CI for GMTs/GMCs will be obtained within each group separately. The 95% CI for the mean of log-transformed titre/concentration will be first obtained assuming that log-transformed values were normally distributed with unknown variance. The 95% CI for the GMTs/GMCs will then be obtained by exponential-transformation of the 95% CI for the mean of log-transformed titre/concentration.

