- Control: placebo control
- Vaccination schedule:
 - All subjects will receive a single dose of *Boostrix* or placebo at 27-36 weeks (i.e. completed 27 weeks until 36 weeks) of gestation (Visit 1). Subjects who receive *Boostrix* at Visit 1 will receive a dose of placebo post-delivery (Visit 3) while those who receive placebo at Visit 1 will receive *Boostrix* post-delivery (Visit 3).
 - *All eligible household contacts of the infants born to pregnant women enrolled in Spain will be eligible to receive a single dose of Boostrix as part of an assessment of cocooning. Although the vaccine can be administered anytime during the study, it is recommended that the vaccine is administered preferably 2 weeks before birth of the infant.*
- Treatment allocation: randomised.
- Blinding: Observer-blind. Refer to Section 5.3 for details of the of blinding procedure.

The blinding of study epoch is presented in [Table 3](#).

Table 3 Blinding of study epoch

Study Epoch	Blinding
Epoch 001	observer-blind

- Sampling schedule: Blood samples will be collected at the following time-points:
 - Pre-Vacc (Visit 1): Before the booster vaccination, approximately 5 mL of blood sample will be collected from all subjects.
 - Post-Vacc (Visit 2): One month after the booster vaccination, approximately 5 mL of blood sample will be collected from all subjects.
 - Cord blood (Visit 3): approximately 2.5 mL of blood sample from the umbilical cord will be collected from all subjects.
- Type of study: self-contained
- Data collection: Electronic Case Report Form (eCRF).
- Safety monitoring: An independent data monitoring committee (IDMC) (including obstetrician, paediatrician, statistician and a neonatologist) will be put in place to oversee the safety aspects of *Boostrix* in the clinical study i.e. each SAE/congenital anomaly/foetal malformation case/incidence of grade 3 local and general solicited adverse events (AEs) will be reviewed by this committee (See Section 5.4.1 for details).

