5.2.2.1.1. Study group and treatment number allocation (Amended: 15 July 2015)

The target will be to enrol approximately 680 eligible subjects who will be randomly assigned to two study groups in a (1: 1) ratio (approximately 340 subjects in each group).

Allocation of the subject to a study group at the investigator site will be performed using a randomisation system on internet (SBIR). The randomisation algorithm will use a minimisation procedure accounting for centre, age (≥ 18 - <25 years, ≥ 25 - <35 years and ≥ 35 - ≤ 45 years), gestational age (27-32 weeks and 33-36 weeks) and country.

Minimisation factors will have equal weight in the minimisation algorithm.

After obtaining the signed and dated ICF from the subject and having checked the eligibility of the subject, the site staff in charge of the vaccine administration will access SBIR. Upon providing the subject identification number, the randomisation system will determine the study group and will provide the treatment number to be used for each dose.

The number of each administered treatment must be recorded in the eCRF on the Vaccine Administration screen.

When SBIR is not available, please refer to the SBIR user guide or the Study Procedures Manual (SPM) for specific instructions.

All the eligible household contacts of infants born to pregnant women enrolled in Spain will be eligible to receive a single dose of Boostrix as part of an assessment of cocooning. For specific instructions with respect to treatment allocation of the household contacts in Spain, refer to the SPM.

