5.7.4. Biological samples evaluation

5.7.4.1. Immunological read-outs

The immunological read-outs are presented in [Table 9](#).

Table 9 Immunological read-outs

Blood sampling time-point		No. subjects	Component	Components priority rank
Type of contact and time-point	Sampling time-point			
Visit 1 (Day 0)	Pre-Vacc	All	PT, PRN and FHA	1
			D, T	2
Visit 2 (Day 30)	Post-Vacc	All	PT, PRN and FHA	1
			D, T	2
Visit 3 (At birth)	At birth	All*	PT, PRN and FHA	1

Pre-vacc: Blood sample to be collected before the dose of the booster vaccination in pregnant women (Visit 1).

Post-vacc: Blood sample to be collected one month after the booster vaccination in pregnant women (Visit 2).

* Cord blood collected from umbilical cord of subjects

In case of insufficient blood sample volume to perform assays for all antibodies, the samples will be analysed according to priority ranking provided in [Table 9](#).

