10.3. Determination of sample size

It is proposed to conduct the study with a sample size of 680 subjects. Assuming a drop-out rate of approximately 20%, to compensate for subject attrition due to early withdrawal, a total of 680 subjects (340 in each group) will be randomised in a 1:1 ratio in order to obtain the desired number of 272 evaluable subjects in each group for immunogenicity analysis. Availability of 272 evaluable subjects per group (for a total of 680 subjects) will provide above 96% overall power to reach the primary endpoint for the primary maternal phase using Bonferroni adjustment on type II error. This sample size is justified by the expected difficulty to enrol pregnant women in the study and on the minimum requirement of safety data in pregnant women, as determined by EU guidelines [EMA, 2008].

Table 16 presents the Power to rule out the null hypothesis (H_0 : group GMC ratio < 1.5) that dTpa Group is not superior to the Control Group.

Table 16 Power to rule out the null hypothesis (H_0 : group GMC ratio < 1.5) that dTpa Group is not superior to the Control Group (N= 272 evaluable subjects per group)

Endpoint	Standard deviation* [Log ₁₀ (titre)]	True group ratio*	Power**
Anti-PT	0.577	2.3	96%
Anti-FHA	0.564	5	>99%
Anti-PRN	0.564	5	>99%

*anticipated conservative value (References: [Leuridan, 2011; Munoz, 2014])

** PASS2005, one sided test for difference between 2 independent groups, H_A : group difference=log10 (true group ratio), one-side alpha = 0.025, Assuming common variance between the groups Using Bonferroni adjustment on type II error (overall beta=sum of type II error of each endpoint)

Table 17 presents the precision achieved with a sample of 300 subjects in each group for the various possible expected adverse pregnancy outcomes and listed pregnancy-related adverse events of interest/neonate-related events of interest in terms of exact 95% CIs.

Table 17 Precision achieved with a sample of 300 subjects in each group for the various possible expected pregnancy outcomes and listed pregnancy-related adverse events of interest/ neonate-related events of interest in terms of exact 95 percent CI

No. of subjects expected (N)	Pregnancy outcome and listed pregnancy-related adverse events of interest/neonate-related events of interest	Subjects with outcome			
		n	%	Exact 95%CI	
				LL	UL
300	Stillbirth	1	0.3	0.0	1.8
	Stillbirth [^]	0	0.0	0.0	1.2
	Placental Abruption	3	1.0	0.2	2.9
	Placenta previa	1	0.3	0.0	1.8

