10.7. Analysis of immunogenicity

The primary analysis will be based on the ATP cohort for analysis of immunogenicity. If, in any vaccine group, the percentage of vaccinated subjects with serological results excluded from this ATP cohort is 5% or more, a second analysis based on the TVC will be performed to complement the ATP analysis.

10.7.1. Within group assessment:

For each treatment group, before and one month after vaccination during pregnancy and if blood sample result is available:

- Seroprotection rates and their exact 95% CIs for antibodies against diphtheria and tetanus will be calculated.
- Seropositivity rates and their exact 95% CIs for antibodies against PT, FHA, PRN, will be tabulated.
- GMCs and their 95% CIs for antibodies against all vaccine antigens will be calculated.
- The distribution of antibody concentrations one month after booster vaccination for each antigen will be displayed using reverse cumulative distribution curves.
- Vaccine response to diphtheria, tetanus and pertussis antigens and their exact 95% CI will be calculated.

In the cord blood sample, if the blood sample result is available:

- Seropositivity rates and their exact 95% CIs for antibodies against PT, FHA, PRN, will be tabulated.
- GMCs and their 95% CIs for antibodies against PT, FHA, PRN antigens will be calculated.

10.7.2. Between group assessment:

- The primary objective is to demonstrate that, the immune response in the dTpa Group is superior to that in the Control Group for the pertussis antigens, in the cord blood sample.
 - *The LL of the 95% CI of the GMC ratio [dTpa Group divided by Control Group] for anti-PT, anti-FHA and anti-PRN antibodies are ≥ 1.5 .*

The CI of the group GMC ratios will be computed using a two-sample t test assuming heterogeneity of variance.

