#### 11.2.4. Immunogenicity

- For a given subject and given immunogenicity measurement, missing or non-evaluatable measurements will not be replaced.
- The Geometric Mean Concentrations (GMCs) calculations are performed by taking the anti-log of the mean of the log titre transformations. Antibody concentrations below the cut-off of the assay will be given an arbitrary value of half the cut-off of the assay for the purpose of GMC calculation.
- A seronegative subject is a subject whose antibody concentration is below the assay cut-off value. A seropositive subject is a subject whose antibody concentration is greater than or equal to the assay cut-off value.

Vaccine response definition:

- Vaccine response to D and T antigens was defined as:
  - for subjects with pre-vaccination concentration < 0.1 IU/mL antibody (ie below the seroprotection cut-off), antibody concentrations at least  $\geq 0.4$  IU/mL, one month after vaccination, and
  - for subjects with pre-vaccination concentration  $\geq 0.1$  IU/mL (ie equal or above the seroprotection cut-off), an increase in antibody concentrations of at least four times the pre-vaccination concentration, one month after vaccination.
- Vaccine response to PT, FHA and PRN antigens was defined as:
  - for subjects with pre-vaccination antibody concentration below the assay cut-off, post-vaccination antibody concentration  $\geq 4$  times the assay cut-off,
  - for subjects with pre-vaccination antibody concentration between the assay cut-off and below 4 times the assay cut-off, post-vaccination antibody concentration  $\geq 4$  times the pre-vaccination antibody concentration, and
  - for subjects with pre-vaccination antibody concentration  $\geq 4$  times the assay cut-off, post-vaccination antibody concentration  $\geq 2$  times the pre-vaccination antibody concentration.

The thresholds defining seropositivity are provided below as per new re-validated assay are the following.

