**Immunogenicity:**

- For a given subject and a given immunogenicity measurement time point, missing or non-evaluable measurements will not be replaced.

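### Optional gain, not an error: adjusting the primary cord-blood GMC ratio for the pre-vaccination titre would narrow the anti-PT interval if baseline and cord levels correlate

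*SAP*

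**What the plan says.** The primary criterion is a lower 95% limit of at least 1.5 for the cord-blood GMC ratio, for anti-PT, anti-FHA and anti-PRN alike (Protocol 2.1, SAP 3). Protocol 10.7.2 gives the method: "The CI of the group GMC ratios will be computed using a two-sample t test assuming heterogeneity of variance". SAP 6.3.1.2 repeats it. SAP 11.1 describes an ANOVA on log10 concentrations, "The ANOVA model will include the vaccine group as fixed effects", together with Welch's test. No covariate is named.

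The baseline data are already in the design. Protocol 3 states: "Before the booster vaccination, approximately 5 mL of blood sample will be collected from all subjects". Protocol 5.7.4.1 says that if volume is short, "the samples will be analysed according to priority ranking provided in" Table 9, where PT, PRN and FHA hold rank 1 at Visit 1 for all subjects. Allocation also used prognostic information: "The randomisation algorithm will use a minimisation procedure accounting for centre, age", gestational age and country (Protocol 5.2.2.1.1). None of these factors enters the primary model.

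Two data rules bear on any adjustment. SAP 11.2.4 says: "Antibody concentrations below the cut-off of the assay will be given an arbitrary value of half the cut-off of the assay". SAP 11.2.6 says: "For a given subject and a given immunogenicity measurement time point, missing or non-evaluable measurements will not be replaced".

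**The concern.** All three antigens must pass, so the weakest one sets the chance of success. Protocol Table 16 plans a ratio of 2.3 for anti-PT and of 5 for the other two. Anti-FHA and anti-PRN have power near 100% and gain almost nothing from a tighter interval. Anti-PT has the least room above 1.5.

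A baseline covariate removes the part of the between-woman variation in cord levels that was present before vaccination. It also reduces the effect of any chance imbalance in baseline titre between the groups. What is at stake is some precision on anti-PT, not the validity of the result.

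**Working it through.** **Inputs.** From Protocol 10.3 and Table 16: anti-PT log10 SD 0.577, true ratio 2.3, null ratio 1.5, 272 evaluable per group, one-sided alpha 0.025, common variance. The baseline-to-cord correlation is not in the documents and is treated as an assumed range starting at zero.

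**1. The plan's own figure.**
- Difference to detect: log10(2.3/1.5) = 0.1856.
- SE = 0.577 × √(2/272) = 0.0495.
- Power (noncentral t, 542 df) = 96.3%. The protocol states 96%, so it reproduces.
- Half-width = 1.964 × 0.0495 = 0.0972 on the log10 scale. The observed ratio must reach 1.5 × 10^0.0972 = 1.88.

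**2. Effect of adjustment, closed form.** With 1:1 allocation the common slope is the average of the two arms' slopes. If the arm SDs are equal, the residual SD is 0.577 × √(1 − r²), where r is the mean of the two within-arm correlations.

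| r | SE | Interval narrower by | Required observed ratio | Power at 2.3 |
|---|---|---|---|---|
| 0 | 0.0495 | 0% | 1.88 | 96.3% |
| 0.2 | 0.0485 | 2.0% | 1.87 | 96.9% |
| 0.3 | 0.0472 | 4.6% | 1.86 | 97.5% |
| 0.4 | 0.0453 | 8.3% | 1.84 | 98.3% |
| 0.5 | 0.0428 | 13.4% | 1.82 | 99.1% |

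If the true anti-PT ratio were 2.0 (assumption), power would go from 71.3% unadjusted to 75.3% at r = 0.3.

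**3. Simulation of the full model.** This used 4,000 trials per cell, HC2 standard errors, six countries and 3% missing baselines filled with the mean plus an indicator. All of these settings are assumptions. Vaccination falls between the two samples and may weaken the correlation in the dTpa arm, so the arms were allowed to differ. Baselines below the cut-off entered at half the cut-off. Change in interval width:

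| Correlation, placebo / vaccinated | 0% below cut-off | 40% below cut-off |
|---|---|---|
| 0 / 0 | 0.2% wider | 0.2% wider |
| 0.4 / 0 | 1.7% narrower | 1.5% narrower |
| 0.6 / 0 | 4.2% narrower | 3.7% narrower |
| 0.6 / 0.2 | 7.9% narrower | 6.8% narrower |
| 0.6 / 0.6 | 19.2% narrower | 16.4% narrower |

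**4. Unequal arm SDs.** The Welch test was chosen to allow these. In large samples the variance is multiplied by 1 − 2b²/(s_v² + s_p²), where b is the mean of the two arms' slopes per SD of baseline. For correlations 0.6 / 0:
- Equal SDs (both 1): b = 0.3, factor 1 − 0.18/2 = 0.91, interval 4.6% narrower.
- Vaccinated SD 1.5 times placebo (assumed): b = 0.3, factor 1 − 0.18/3.25 = 0.945, interval 2.8% narrower.
- Placebo SD 1.5 times vaccinated (assumed): b = 0.45, factor 1 − 0.405/3.25 = 0.875, interval 6.4% narrower.

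**5. Error rate and downside.** At a true ratio of 1.5 (20,000 trials, 40% below cut-off) the success rates, adjusted against Welch, were 2.48% against 2.49% (0/0), 2.66% against 2.63% (0.6/0) and 2.46% against 2.48% (0.6/0.6). The nominal rate is 2.5%, with Monte Carlo SE 0.11%. In the worst case, with uninformative and unbalanced covariates, the interval was 0.9% wider. By the formula that puts power at about 96.0%, against 96.3% unadjusted.

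**6. Missing baselines.** The ATP immunogenicity cohort requires cord serology, not a baseline result (SAP 5.1.3 and 5.2.1.1). Dropping 3% of women for a missing baseline leaves 264 per arm and takes unadjusted power to 95.8%. Complete-case adjustment only breaks even when the missing share is about r², so a covariate rule is needed.

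**The case against.** The strongest reply is that the planned test is correct, consistent across both documents and adequately powered, so replacing it is a preference. The gain rests on a correlation nobody has supplied. At r = 0.3 it is 1.2 power points, and the required ratio moves only from 1.88 to 1.86. The 2.0 scenario assumes a ratio below a planning value that Table 16 already marks as an "anticipated conservative value". The change also touches the primary success criterion late: the SAP is dated February 2018, and SAP 6.1.2 shows that some data were already in hand. A new primary estimator at that stage invites questions about data-driven choice.

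Much of this stands. The benefit is modest at planning values and could be nil, and its size depends on the arm SDs as well as the correlation. The documents do not show whether unblinding has occurred. If it has, the primary analysis should stay unadjusted. The replacement of centre by country also means that the model matches the allocation only in part.

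The reply does not remove the point. The planning SD predates the re-developed pertussis assays in SAP 9, and no updated SD is given. If the SD were 0.65 (assumption), power at 2.3 would be 91.4% unadjusted, 93.6% at r = 0.3 and 95.2% at r = 0.4. Adjustment therefore helps most where the planning values fail, and costs under about 1% in width where it does not help. Unequal SDs change the size of the gain but not its direction.

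**Conclusion.** The point holds as an optional improvement. The unadjusted analysis is sound, and its 96% power reproduces. Baseline adjustment would leave the target ratio and the error rate unchanged. It would narrow the anti-PT interval by roughly 2 to 8% for mean arm correlations of 0.2 to 0.4, and by more only if the correlation survives vaccination in the dTpa arm. Anti-FHA and anti-PRN are essentially unaffected in power.

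All the gains quoted come from the baseline titre and rest on assumed correlations. The minimisation factors are included only to bring the analysis closer to the allocation.

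**What to change.** Before unblinding, amend SAP 6.3.1.2 and 11.1 as follows:

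- Primary model: log10 cord concentration on group, log10 pre-vaccination concentration of the same antigen, gestational-age stratum, maternal-age stratum and country, with HC2 robust standard errors to keep the allowance for unequal variances. Country stands in for centre, whose cells may be sparse. Take the lower limit for the 1.5 criterion from this model.
- Missing baselines: in SAP 11.2.6, fill the covariate with its mean and add a missingness indicator, so that no woman with a cord result is lost. Outcome values stay unreplaced.
- Baselines below the cut-off enter at half the cut-off, as in SAP 11.2.4.
- Keep the unadjusted Welch interval as the sensitivity analysis.
- Record the change in SAP 9 and justify it in the study report, as Protocol 10.10 requires.

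The footnote to SAP Template 11 already calls the ratio adjusted although SAP 11.1 names no covariate. The same edit should reconcile the two.

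The cost is a little SAP text, a justification in the report and minor programming. No new samples, assays or visits are needed. The sponsor should also decide whether a change to the primary analysis needs a protocol amendment.
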